10.1 Protection of Personally Identifiable Information

The Sponsor respects and protects personally identifiable information collected or maintained for this clinical study. The privacy of each subject and confidentiality of his/her information will be preserved in reports and when publishing any data. Confidentiality of data will be observed by all parties involved at all times throughout the clinical study. All data will be secured against unauthorized access.

10.2 Data Management Plan

A Data Management Plan (DMP) will describe procedures used for data review, database cleaning, and issuing and resolving data queries. If appropriate, the DMP may be updated throughout the clinical study duration. All revisions will be tracked and document controlled.

Subject data will be captured in a validated electronic data capture (EDC) system hosted by the Sponsor.

Only authorized site personnel will be permitted to enter the CRF data through the EDC system deployed by the Sponsor. An electronic audit trail will be used to track any subsequent changes of the entered data.

10.3 Document and Data Control

10.3.1 Traceability of Documents and Data

The investigator will ensure accuracy, completeness legibility and timeliness of the data reported to the Sponsor on the CRFs and in all required reports.

10.3.2 Recording Data

The CRF will be reviewed by the authorized site personnel. An appropriate comment will be provided to explain changes to data reported on the CRF.

11 Monitoring

It is the responsibility of the Sponsor to ensure the clinical study is conducted, recorded and reported according to the approved CIP, subsequent amendment(s), applicable regulations and guidance documents.

Centralized monitoring will occur through routine internal data review. This monitoring is designed to identify missing and inconsistent data, data outliers, and potential CIP deviations that may be indicative of site non-compliance. On-site monitoring may occur at the discretion of the Sponsor.

12 Compliance Statement

12.1 Statement of Compliance

This clinical study will be conducted in compliance with the most current regional and local laws and regulations. Principles of Good Clinical Practice will be followed as based on the most current version of the World Medical Association (WMA) Declaration of Helsinki.

The investigator will sign a Clinical Trial Agreement and agrees to be compliant with it. The investigator will not start enrolling subjects or requesting informed consent from any subject prior to obtaining IRB/EC approval and relevant Regulatory Authority approval, if applicable, and authorization from the Sponsor in writing for the clinical study. If additional requirements are imposed by the IRB/EC or relevant Regulatory Authority, those requirements will be followed. If any action is taken by an IRB/EC or a relevant Regulatory Authority with respect to the clinical study, that information will be forwarded to the Sponsor.

The Sponsor has taken up general liability insurance in accordance with the requirements of the applicable local laws. An appropriate Sponsor country representative will be utilized to understand the requirements for the type of insurance that will be provided for subjects, and such information will be incorporated into the site informed consent, as applicable. If required, additional subject coverage or a clinical study specific insurance will be provided by the Sponsor.

12.2 Quality Assurance Audits and Regulatory Inspections

The investigator and/or delegate should contact the Sponsor immediately upon notification of a regulatory authority inspection at the site. A monitor or designee will assist the investigator and/or delegate in preparing for the audit. The Sponsor may perform quality assurance audits, as required.

The Principal Investigator or institution will provide direct access to source data during and after the clinical study for monitoring, audits, IRB/EC review and regulatory authority inspections, as required. The Principal Investigator or institution will obtain permission for direct access to source documents from the subject, hospital administration and national regulatory authorities before starting the clinical study.

12.3 Repeated and Serious Non-Compliance

In the event of repeated non-compliance or a one-time serious non-compliance, as determined by the Sponsor, a monitor or designee will attempt to secure compliance by one or more of the following actions:

- Visiting the investigator,
- Contacting the investigator by telephone,
- Contacting the investigator in writing,
- Retraining of the investigator.

If an investigator is found to be repeatedly non-compliant with the signed agreement, the CIP or any other conditions of the clinical study, the Sponsor will either secure compliance or, at its sole discretion, terminate the investigator's participation in the clinical study. In case of termination, the Sponsor will inform the responsible regulatory authority, as required, and ensure that the IRB/EC is notified, either by the Principal Investigator or by the Sponsor.

13 Suspension or Premature Termination of the Clinical Study

The Sponsor reserves the right to terminate the clinical study at any stage, with appropriate written notice to the investigators, IRB/ECs and relevant Regulatory authorities, if required.

A Principal Investigator, IRB/EC or regulatory authority may suspend or prematurely terminate participation in a clinical study at the investigational sites for which they are responsible. The investigators will follow the requirements specified in the Clinical Trial Agreement.

If suspicion of an unacceptable risk to subjects arises during the clinical study or when so instructed by the IRB/EC or regulatory authority, the Sponsor may suspend the clinical study while the risk is assessed. The Sponsor will terminate the clinical study if an unacceptable risk is confirmed. If the Sponsor completes an analysis of the reasons for the suspension, implements the necessary corrective actions, and decides to lift the temporary suspension, the Sponsor will inform the Principal Investigators, IRB/EC, or regulatory authority, where appropriate, of the rationale, providing them with the relevant data supporting this decision. Approval from the IRB/EC or regulatory authority, where appropriate, will be obtained before the clinical study resumes. If subjects have been informed of the suspension, the Principal Investigator or authorized designee will inform them of the reasons for resumption.

If the Sponsor suspends or prematurely terminates the clinical study at an individual investigational site in the interest of safety, the Sponsor will inform all other Principal Investigators.

If suspension or premature termination occurs, the Sponsor will remain responsible for providing resources to fulfill the obligations from the CIP and existing agreements for following up the subjects enrolled in the clinical study, and the Principal Investigator or authorized designee will promptly inform the enrolled subjects at his/her investigational site, if appropriate.

14 Clinical Study Conclusion

The clinical study will be concluded when:

- All sites are closed AND
- The final report has been provided to investigators or the Sponsor has provided formal documentation of clinical study closure.

15 Publication Policy

Publications or presentations of clinical study methods or results will adhere to Sponsor's publication policy, which is based on Good Publication Practices and International Committee of Medical Journal Editors (ICMJE) guidelines. A copy of the policy will be provided upon request of the investigator. Publication planning and authorship determinations will be overseen by Publications Committee (see section 6.9.1), and investigators will be notified via email about the dissemination of study data and opportunities for involvement as authors on publications/presentations.

16 Reporting Results on ClinicalTrials.gov Website

This clinical study will be registered on ClinicalTrials.gov and results will be posted on ClinicalTrials.gov as required.

Appendix A: CIP Revisions

Procedure for CIP Amendments

This CIP may be amended as appropriate by the Sponsor. Rationale will be included with each amended version in the revision history table below. The version number and date of amendments will be documented.

The acknowledgement of the amended CIP by the Principal Investigators will be collected on the signature pages.

IRB/EC and relevant Regulatory Authorities, if applicable, will be notified of amendments to the CIP.

Revision History

A horizontal table with a blue header row and several blacked-out rows below. The header row contains four columns with the first three being very narrow and the fourth being wider. The rows below are completely blacked out, obscuring any text that might have been present.

Appendix C: Definitions

Non-study Specific Definitions

Vulnerable Subject

Vulnerable subject is defined as individual whose willingness to volunteer in a clinical investigation could be unduly influenced by the expectation, whether justified or not, of benefits associated with participation or of retaliatory response from senior members of a hierarchy in case of refusal to participate.

EXAMPLE Individuals with lack of or loss of autonomy due to immaturity or through mental disability, persons in nursing homes, children, impoverished persons, subjects in emergency situations, ethnic minority groups, homeless persons, nomads, refugees, and those incapable of giving informed consent. Other vulnerable subjects include, for example, members of a group with a hierarchical structure such as university students, subordinate hospital and laboratory personnel, employees of the Sponsor, members of the armed forces, and persons kept in detention.

Complaint

Any written, electronic or oral communication that alleges deficiencies related to the identity, quality, durability, reliability, safety, effectiveness or performance of a device after it is released for distribution.

Study Specific Definitions

Arrhythmia recurrence

For the purpose of this clinical study, recurrence of arrhythmia is deemed to have occurred only when the arrhythmia is documented on ECG or during a period of monitoring e.g. Holter-monitoring, implantable cardiac monitor, ICD, CRT... Atrial arrhythmias must be 30 seconds or longer. Ventricular arrhythmias are any treated by ICD or 20 seconds or longer.

Blanking period (AF only)

The 3-month (90 days) period of time following a procedure in which AF episodes can occur as part of the body's healing response. Any arrhythmia activity during that blanking period is not counted in the study's results and is not used in determining success or failure of the procedure.

Acute success

For the purpose of this study, acute success is attained when one (or multiple) predefined procedural endpoints, have been realized. These predefined procedural endpoints include, but are not limited to:

- Abolition of all clinical ventricular ectopies and unstable ventricular arrhythmias
- Bidirectional block across CTI
- Block across mitral isthmus
- Confirmation of vagal reflexes
- CS isolation
- Documentation of block at a critical isthmus of conduction
- Elimination and noninducibility of tachycardia following ablation
 - o With burst pacing
 - o With Isoproterenol
 - o With programmed atrial and ventricular stimulation
- Elimination of dormant conduction
- Elimination of LAVA
- Elimination of local Purkinje potentials
- Lines connecting scar to anatomic conduction barrier
- Lines parallel to scar border zone

- Pulmonary Vein capture with exit block
- Pulmonary Vein electrical isolation
- Scar homogenization
- Superior Vena Cava isolation
- Termination of tachycardia during RF energy application

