6.3.3 Scheduled Follow-ups

In-clinic follow-up visits are scheduled at 1 month, 6 months and 12 months after procedure. The scheduled visit windows are calculated from the index procedure.

6.3.3.1 1-Month Visit (within 30 days from procedure)

The 1-month visit needs to be performed within 30 days post procedure, depending on the hospital's standard practice for 1st follow-up post procedure.

The following information is collected:

- Arrhythmia recurrence
 - o For the purpose of this clinical study, recurrence of arrhythmia is deemed to have occurred only when the arrhythmia is documented on ECG or during a period of monitoring e.g. holter-monitoring or implantable cardiac monitor. Atrial arrhythmias 30 seconds or longer will be collected. Ventricular arrhythmias treated by an ICD, or lasting 20 seconds or longer will be collected.
- Antiarrhythmic / Anticoagulant medication
- Healthcare Utilization information when applicable
- Protocol deviation, when applicable

6.3.3.2 6- and 12-Month Visit (\pm 30 days)

At each visit, the following information is collected:

- Arrhythmia recurrence
 - o For the purpose of this clinical study, recurrence of arrhythmia is deemed to have occurred only when the arrhythmia is documented on ECG or during a period of monitoring e.g. Holter-monitoring or implantable cardiac monitor. Atrial arrhythmias 30 seconds or longer will be collected. Ventricular arrhythmias treated by an ICD, or lasting 20 seconds or longer will be collected.
- Antiarrhythmic / Anticoagulant medication
- Completion of the EQ-5D questionnaire

- Holter monitoring* at 12-Month visit (for patients treated for AF)
- Healthcare Utilization information when applicable
- Protocol deviation, when applicable

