***Holter Monitoring (AF only)**

Subjects with AF will be issued a holter monitor at the 12-month visit and instructed to obtain a 48-hour recording. A core laboratory will review each recording and report findings to the Sponsor.

NOTE: The Sponsor may request access to other patient data during the required protocol follow up visits or throughout the follow up period, which may include, but is not limited to, data from implanted device(s).

Record the required information on the appropriate CRF(s). Documentation of arrhythmia (e.g. ECG printouts, holter printouts, session records), where applicable, should be retrieved and submitted electronically through EDC to the Sponsor.

Sponsor representatives can be involved in providing support during the follow-up procedures.

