- Mapping points per minute used will be summarized (e.g. as mean, median, standard deviation, minimum and/or maximum) across arrhythmia types and for each type of arrhythmia per catheter as appropriate, with following map types:
 - o Manual mapping
 - o AutoMap
 - o Combination Manual Map / AutoMap
 - o TurboMap™

Rate of acute success based on pre-defined procedural endpoints (refer to Appendix C):

- The number and proportion of subjects with acute success will be summarized.

Freedom from arrhythmia recurrence: Arrhythmia recurrence is defined as documented atrial arrhythmia for 30 seconds or longer or documented ventricular arrhythmia either treated by ICD or lasting 20 seconds or longer throughout the follow-up period.

- This analysis will be performed using the Kaplan-Meier (KM) analyses. The start date is the date of the index procedure. For subjects who do not experience an event, their follow up duration will be defined from the start date to the date of death, withdrawal, or last follow-up, whichever occurred later.
- Time to arrhythmia recurrence is defined as time from index procedure to the date of the first recurrence. For subjects with AF, events occurring within the blanking period (defined as the first 90 days after the index procedure) will be excluded from the analysis.

Number of repeat ablations up to 12 months. This will be summarized as:

- Total count of repeat ablations up to 12 months among all subjects in the analysis population defined in section 7.1.3
- Total number of subjects who experience at least one repeat ablation up to 12 months among all subjects in analysis population defined in section 7.1.3

Summary of NavX Patch placement locations used

- The number and proportion of subjects with NavX patches (Surface Electrode Patches) placed by location

Number of gaps in lesions identified during the procedure that require touch-up ablation:

- The number and proportion of subjects with gaps in lesions identified will be summarized and reported.
- The summary of number of gaps identified will be reported.
- The number and proportion of subjects where the AutoMark Module assisted in identifying these gaps will be summarized and reported.

Changes in EQ-5D quality of life score at 6 and 12 months:

- Changes in EQ-5D at 6 months from baseline, and changes in EQ-5D score at 12 months from baseline will be summarized.

Number of unscheduled visits and hospitalizations due to arrhythmia:

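### ECG counts as documentation of recurrence, but the 30 s / 20 s minimum makes no provision for an arrhythmia that fills a shorter ECG; read literally, such events are lost or dated late

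*Combined protocol and SAP*

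**What the plan says.** **Sources.** Appendix C states that "recurrence of arrhythmia is deemed to have occurred only when the arrhythmia is documented on ECG or during a period of monitoring", and gives Holter and implanted devices as examples of monitoring. Sections 6.3.3.1 and 6.3.3.2 repeat the ECG route for each follow-up visit.

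**Duration.** Appendix C continues: "Atrial arrhythmias must be 30 seconds or longer". For the ventricular case it says "Ventricular arrhythmias are any treated by ICD or 20 seconds or longer". No recording type is exempted.

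**Collection.** Sections 6.3.3.1 and 6.3.3.2 phrase the same thresholds as a data-collection rule: "Atrial arrhythmias 30 seconds or longer will be collected", with the matching ventricular rule.

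**Analysis.** Section 7.1.1 defines the Kaplan-Meier event: "Arrhythmia recurrence is defined as documented atrial arrhythmia for 30 seconds or longer", or a ventricular arrhythmia that is ICD-treated or lasts at least 20 s. Subjects without an event are censored: "For subjects who do not experience an event, their follow up duration will be defined from the start date", up to death, withdrawal or last follow-up. For AF subjects, events in the first 90 days are excluded.

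**Scheduled long recording.** There is one, for AF subjects only: "Subjects with AF will be issued a holter monitor at the 12-month visit and instructed to obtain a 48-hour recording". It is read by a core laboratory.

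The documents give no ECG length, no method for establishing duration from an ECG, and no rule for an arrhythmia still running when a short tracing ends.

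**The concern.** An ECG is a snapshot. If the tracing is shorter than the threshold and the arrhythmia occupies all of it, the tracing shows only that the episode lasted at least as long as the strip; the true duration is unknown. The plan admits this kind of evidence and then sets a test that the evidence may be unable to pass.

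The cases at risk are the persistent ones, where the subject is in the arrhythmia throughout the recording. These are the clearest recurrences clinically.

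The error has one direction. A rejected ECG turns a recurrence into a censored, event-free subject, or moves the event to a later date. Either raises the reported curve. If some sites accept a full-strip ECG and others do not, the endpoint also differs between centers. And because 6.3.3 limits collection to episodes that reach the threshold, the rejected tracings may not be in the database, so the effect could not be examined afterwards.

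**Working it through.** The plan gives no figure to reproduce here: the visible text has no assumed recurrence rate, and 7.1.1 plans no hypothesis test. The check is a comparison of the passages, followed by an illustration.

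**Step 1. Which wording decides the case?**

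| Place | Wording attaches duration to | Arrhythmia filling a short ECG |
|---|---|---|
| Appendix C | the arrhythmia | duration unknown; neither counted nor excluded |
| 6.3.3.1, 6.3.3.2 | the arrhythmia, as a condition for collection | not shown to qualify, so may not be collected |
| 7.1.1 | the documented arrhythmia | most naturally read as 30 s (20 s) of documentation, so not an event |

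Appendix C is silent on the case. Section 7.1.1, which drives the analysis, leans against counting it.

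**Step 2. When does the conflict arise?** ECG length is an assumption; values from 10 to 60 s were examined.

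| Assumed strip | Can show 30 s (atrial) | Can show 20 s (ventricular) |
|---|---|---|
| 10 or 12 s | no | no |
| 20 or 25 s | no | yes |
| 30 or 60 s | yes | yes |

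The conflict exists only below 30 s for atrial arrhythmias and below 20 s for ventricular arrhythmias not treated by an ICD. ICD-treated episodes count at any duration and are unaffected.

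**Step 3. What happens to the subject?**
- No other documentation: censored as event-free, and the event is lost.
- Caught later by Holter or an implanted device: the event is dated at the later recording, so the curve is too high between the true and recorded dates. The 12-month visit has a window of ±30 days, so a Holter event may even fall after 12 months.

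**Step 4. Illustration of the loss.** Let S be true 12-month freedom and q the share of recurrences resting solely on a too-short ECG. Both are assumed. Ignoring other censoring,

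apparent freedom = 1 − (1 − q)(1 − S), so overstatement = q(1 − S).

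| S | q = 5% | q = 10% | q = 20% | q = 30% |
|---|---|---|---|---|
| 60% | 62% | 64% | 68% | 72% |
| 70% | 71.5% | 73% | 76% | 79% |
| 80% | 81% | 82% | 84% | 86% |

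Smallest overstatement: 0.05 × 0.20 = 1 point. Largest: 0.30 × 0.40 = 12 points. If full-strip arrhythmias count, q = 0 and this bias disappears.

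**The case against.** The strongest reply is that there is no contradiction. Appendix C asks that the arrhythmia last 30 s, not that a single tracing display 30 s, and an investigator may reasonably conclude that an arrhythmia filling an ECG lasted longer. A reader might infer that such an ECG can never meet the definition and always counts as no recurrence; the documents do not go that far. What stands against the reply is that 7.1.1 is worded differently from Appendix C, and nothing says which reading governs.

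Second, strip length is nowhere stated. The follow-up text says ECG without a lead count; the only 12-lead ECG in the schedule is at baseline. Rhythm strips, serial tracings or telemetry during unscheduled care could show 30 s. This is correct and makes the size unknowable from the documents.

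Third, a reader might infer that ECG is the main route by which recurrence will be seen. The documents do not support that: Table 3 schedules no follow-up ECG, and Holter recordings and implanted-device data are also evidence. But subjects not treated for AF have no scheduled long recording, so without a device or unscheduled monitoring ECG is the route left to them.

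Fourth, a persistent arrhythmia may be recorded again later, and early AF tracings fall in the blanking period anyway. Both points reduce the number of events lost. Neither removes late dating.

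Fifth, the study is descriptive and this is one of twelve listed endpoints, so no test or visible decision depends on it. True, but in a descriptive study the estimate is the result. The case report forms are held separately and may already address the point.

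**Conclusion.** The point holds as a gap in the endpoint definition with a one-directional bias. ECG is an accepted source, one minimum duration applies to all sources (with the ICD-treated exception), and no rule covers an arrhythmia present throughout a shorter ECG. On the literal reading of 7.1.1 such an event is lost if nothing else documents it and late if something does. Both inflate freedom from recurrence.

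The conclusion depends on strips shorter than 30 s (atrial) or 20 s (ventricular), for example an assumed 10 s. If sites record 30 s or more, there is no effect. The 1 to 12 points are illustrative: they rest on assumed values of q (5–30%) and S (60–80%), and on the affected subjects having no later documentation. A reader might be tempted to larger figures by supposing that up to half of recurrences rest on a short ECG; nothing in the documents supports such a share, and the later Holter and device recordings argue against it.

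**What to change.** In Appendix C, 6.3.3.1, 6.3.3.2 and 7.1.1, use one identical definition:
- an arrhythmia present throughout an entire ECG recording that is shorter than the threshold counts as a documented recurrence, outside the blanking period for AF subjects;
- the 30 s and 20 s thresholds apply to Holter, implanted-device and other continuous recordings;
- the ICD-treated rule is unchanged.

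Amend the collection sentence in 6.3.3.1 and 6.3.3.2 so that these tracings are submitted. Record the documentation source and strip length for each event, and add to 7.1.1 a sensitivity analysis that excludes events resting only on a short ECG.

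The cost is a sentence in four places, two data fields and one extra analysis, with no added visit. Some episodes that would have stopped before 30 s may be counted, and the reported freedom figure may be slightly less favourable; the sensitivity analysis shows by how much.
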